14.11.11. Pharmacodynamic Figures

14.11.11.1. Part A

No.	Population	IDSL / Example Shell	Title	Programming Notes	Deliverable
Serum Target Engagement					
4.01.	Safety	PK16	Part A: Individual Free & Total Serum CCL17 Concentration-Time Plots (Linear and Semi-log)	
One panel per dose group.
 
Add the following footnotes:
 
Note: Free CCL17 LLOQ = 2.93 pg/mL, ULOQ = 3600 pg/mL.
 
Note: Total CCL17 LLOQ = 13.11 pg/mL, ULOQ = 50000 pg/mL.
 
Note: The baseline value is presented at an actual relative time of 0 days.
 
Note: Any non-quantifiable (NQ) Free CCL17 concentration values have been set to $\frac{1}{2}^*\text{LLOQ}$.
 
Note: Any NQ Total CCL17 concentration values before the first measurable concentration have been set to 0 and have been included in the linear plot.
 
Note: Any single NQ values have been omitted.
 
Note: Any multiple mid-profile NQ concentrations of Free CCL17 and Total CCL17 have been set to $\frac{1}{2}^*\text{LLOQ}$ and 0, respectively, and the subsequent measurable concentrations have been retained.
 
Note: Percentage reduction values ≤ 0 are imputed to be 0.1 and values ≥ 100 are imputed to be 99.9
	Part A SAC

No.	Population	IDSL / Example Shell	Title	Programming Notes	Deliverable
4.02.	Safety	PK17	Part A: Mean Free & Total Serum CCL17 Concentration-Time Plots (Linear and Semi-log)	
Apply logit transformation for % reduction parameter.
 
If % reduction ≤ 0, set to 0.1.
 
If % reduction ≥ 100, set to 99.9.
 
These imputations are needed for logit transformation.
 
Use Student's t-distribution for CI.
 
Add the following footnotes:
 
Note: Free CCL17 LLOQ = 2.93 pg/mL, ULOQ = 3600 pg/mL.
 
Note: Total CCL17 LLOQ = 13.11 pg/mL, ULOQ = 50000 pg/mL.
 
Note: Free CCL17 and Total CCL17 concentrations below LLOQ have been set to $\frac{1}{2} \times \text{LLOQ}$ and 0, respectively, and have been included in the summary statistic calculations.
 
Note: Any single mid-profile non-quantifiable (NQ) concentrations have been omitted.
 
Note: Measurable Total CCL17 concentrations following more than one consecutive mid-profile NQ have been omitted.
 
Note: Zero Total CCL17 concentration values have been set to missing in the log-linear plot.
 
Note: The geometric mean is plotted as the data is not normally distributed.
 
Note: Percentage reduction values ≤ 0 are imputed to be 0.1 and values ≥ 100 are imputed to be 99.9.
 
Note: The percentage reduction parameter was logit transformed, summarised, and back-transformed using the logistic function to obtain the geometric summary statistics.
	Part A SAC

No.	Population	IDS / Example Shell	Title	Programming Notes	Deliverable
4.03.	Safety	PK18	Part A: Median Free & Total Serum CCL17 Concentration-Time Plots (Linear and Semi-log)	
.Add the following footnotes:
 
Note: Free CCL17 LLOQ = 2.93 pg/mL, ULOQ = 3600 pg/mL.
 
Note: Total CCL17 LLOQ = 13.11 pg/mL, ULOQ = 50000 pg/mL.
 
Note: Free CCL17 and Total CCL17 concentrations below LLOQ have been set to $\frac{1}{2}^*\text{LLOQ}$ and 0, respectively, and have been included in the summary statistic calculations.
 
Note: Any single mid-profile non-quantifiable (NQ) concentrations have been omitted.
 
Note: Measurable Total CCL17 concentrations following more than one consecutive mid-profile NQ have been omitted.
 
Note: Zero Total CCL17 concentration values have been set to missing in the log-linear plot.
	Part A SAC

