4.4.2. Part B

The dose to be administered in Part B was revised (protocol amendment 3) according to the actual PK and TE (% reduction from baseline in free CCL17 levels) data obtained from Part A [GSK Document Number 2019N397787_00]. However, re-analysis of the concentration of GSK3858279 in Part A samples using an improved analytical method [see GSK Document Number RPS-CLIN-004032] has led to a further protocol amendment (number 5). The data from Part A and the recommendation of the dose regimen for Part B are summarised here.

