14.11.10. Pharmacodynamic Tables

14.11.10.1. Part A

No.	Population	IDSL / Example Shell	Title	Programming Notes	Deliverable
Serum Target Engagement					
4.01	Safety	PD_T1	Part A: Summary of Free & Total CCL17 in Serum Concentration- Time Data (pg/mL)	
Please only present the median, min, max, sd (log), geometric mean and 95% CI back-transformed from the \log_e scale.
 
Apply logit transformation for % reduction parameter and present median, min, max, sd (logit), geometric mean and 95% CI, back-transformed from the logit scale.
 
If % reduction ≤ 0, set to 0.1.
 
If % reduction ≥ 100, set to 99.9.
 
These imputations are needed for logit transformation.
 
Use Student's t-distribution for CI.
 
Add the following footnotes:
 
Note: Free CCL17 values below the LLOQ have been imputed to $\frac{1}{2}^*$ LLOQ. Total CCL17 values below the LLOQ have been imputed to 0. Values equal to zero at baseline have been imputed to LLOQ whilst missing baseline values have been imputed to the median of the non-missing baseline values.
 
Note: Free CCL17 and Total CCL17 exceeding the upper limit of quantification (ULOQ) have been excluded from the summary statistics (ULOQ Free CCL17: 3600 pg/mL, ULOQ Total CCL17: 50000 pg/mL).
 
Note: If more than 30% of values have been imputed at any timepoint for a treatment group, then the standard deviation is not displayed.
 
Note: Percentage reduction values ≤ 0 are imputed to be 0.1 and values ≥ 100 are imputed to be 99.9.
 
Note: The percentage reduction parameter was logit transformed, summarised, and back-transformed using the logistic function to obtain the geometric summary statistics. The 95% CI of the geometric mean was calculated using Student's t distribution.
	Part A SAC

No.	Population	IDSL / Example Shell	Title	Programming Notes	Deliverable

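### The single-NQ omission footnote in SAP Figures 4.01–4.06 also covers free CCL17, where an isolated post-dose NQ on active drug is the largest observable effect; it conflicts with the half-LLOQ footnote and biases the plotted mean upward

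*SAP*

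**What the plan says.** **Mean and median figures (SAP 14.11.11, Figures 4.02, 4.03, 4.05, 4.06).** Values below the LLOQ are set to half LLOQ for free CCL17 and to zero for total CCL17, and "have been included in the summary statistic calculations". The next footnote reads: "Any single mid-profile non-quantifiable (NQ) concentrations have been omitted". It names neither analyte. The footnote after it is explicitly limited to total CCL17: "Measurable Total CCL17 concentrations following more than one consecutive mid-profile NQ have been omitted".

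**Individual figures (4.01, 4.04).** Any free NQ value is set to half LLOQ, but a later footnote adds: "Any single NQ values have been omitted". Here even the mid-profile restriction is missing. Multiple mid-profile NQs are kept at half LLOQ (free) or zero (total), and measurable values after them are retained.

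**Tables 4.01 and 4.06 (SAP 14.11.10).** "Free CCL17 values below the LLOQ have been imputed to" half the LLOQ. No footnote omits single NQs.

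**Drug-concentration figures 3.02 and 3.03 (SAP 14.11.9.1).** The single mid-profile omission appears in the same words for serum GSK3858279.

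**Direction of effect.** Protocol Section 4.4.2 expresses target engagement as "TE (% reduction from baseline in free CCL17 levels", so a fall in free CCL17 is the drug effect.

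**The concern.** For drug concentration, an isolated NQ between two measurable levels is suspect, and dropping it is defensible. Free CCL17 moves the other way: it is expected to fall when the antibody binds it and to recover later. A participant who is below the LLOQ at one visit and measurable on either side may simply have reached the nadir there. The rule removes that point because of its value, so at that visit the mean comes from the less suppressed participants.

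There is also a problem of reproducibility. One footnote includes free NQs at half LLOQ and the next omits some of them. Two programmers could draw different figures, and a figure could show a different geometric mean from the table for the same time point. Target engagement is a secondary objective in both parts, and these figures display its depth and time course.

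**Working it through.** The plan states no figure on this point, so there is nothing to reproduce. The check compares the two rules at a single time point.

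**Inputs**
- LLOQ: "Free CCL17 LLOQ = 2.93 pg/mL, ULOQ = 3600 pg/mL" (SAP 14.11.11.1). Half LLOQ is 2.93 / 2 = 1.465 pg/mL.
- Statistic in the mean figures: "The geometric mean is plotted as the data is not normally distributed".
- n = 6 active participants per Part A cohort (Protocol 4.2).
- k = number of participants with an isolated mid-profile NQ at that time point. Not given; varied from 1 to 3.
- G = geometric mean (GM) of the other n − k values. Not given; at least 2.93 if they are all measurable.

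**Formula**
- Table rule, NQs kept: GM = 1.465^(k/n) × G^((n−k)/n).
- Figure rule, isolated NQs dropped: GM = G.
- Ratio of figure to table = (G / 1.465)^(k/n).

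**Lower bound.** When the other values are measurable, G ≥ 2.93 = 2 × 1.465, so the ratio is at least 2^(k/n). This needs no assumption about the distribution above the LLOQ. The last three columns assume a value for G.

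| k of 6 | Minimum ratio | G = 5 | G = 10 | G = 20 |
|---|---|---|---|---|
| 1 | 1.12 | 1.23 | 1.38 | 1.55 |
| 2 | 1.26 | 1.51 | 1.90 | 2.39 |
| 3 | 1.41 | 1.85 | 2.61 | 3.69 |

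Worked case, k = 2 and G = 10 pg/mL: the table GM is (1.465² × 10⁴)^(1/6) = 5.27, the figure GM is 10.0, and the ratio is 1.90.

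**Consecutive NQs are kept, which dilutes the effect.** With one isolated NQ, three participants within NQ runs (1.465 each) and two at 10 pg/mL, the GMs are 2.78 (kept) and 3.16 (dropped), a ratio of 1.14. With one isolated NQ and the other five all within NQ runs, the ratio is 1.00.

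**Larger arm.** With about 25 active participants in Part B (half of 50) and five isolated NQs, the minimum ratio is 2^(5/25) = 1.15.

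**Percentage reduction, Part A only, and only if the omission is carried into it (the footnotes do not say).** For k = 2 and G = 10, the logit-mean reduction with NQs kept versus dropped is 89.0% versus 80.0% at an assumed baseline of 50 pg/mL, 94.6% versus 90.0% at 100, and 98.2% versus 96.7% at 300.

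**Medians.** With six participants and equal remaining values, the median does not move for k = 1 or 2. At k = 3 and G = 10 it goes from 5.73 to 10.

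**After the fix.** With isolated free NQs kept at half LLOQ, figure and table agree on the NQ rule (ratio 1.00).

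**The case against.** The strongest case against is that the rule may rarely bite.

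- **Depth and duration.** Protocol Table 2 predicts 96%, 98% and 99% inhibition at 1, 3 and 10 mg/kg IV. That gives an NQ for baselines below 2.93 / 0.04 = 73, 2.93 / 0.02 = 147 and 2.93 / 0.01 = 293 pg/mL. But those predictions are averages over the first 12 hours, and half-recovery at 10 mg/kg is predicted at 9.5 days. If CCL17 is sampled about as often as drug, deep suppression would produce runs of NQs, which are kept. At 0.1 and 0.3 mg/kg (56% and 86%) an NQ needs a baseline below 2.93 / 0.44 = 6.7 or 2.93 / 0.14 = 21 pg/mL. This stands: a reader might infer that NQ is the usual reading and that the figures misstate suppression generally, or most at doses with brief suppression. The documents support neither inference.
- **Tables.** SAP 10.1.1.1 refers concentration handling to Section 14.5.4, which is not visible. It might apply the omission to the tables too. The mismatch with the tables therefore holds on the visible text only. If 14.5.4 did extend the omission, figures and tables would agree and both would understate suppression.
- **General rule and exception.** The two figure footnotes could be read that way. This reading removes the contradiction but confirms that isolated free NQs are dropped.
- **Other sources.** Derived parameters are tabulated (Tables 4.02, 4.07), concentrations are listed, and Part B percentage reduction is primarily model-derived. This limits the consequence and leaves the figures uncorrected.
- **Total CCL17.** A reader might infer that the omission should go for total CCL17 as well. Total CCL17 rises on drug, so an isolated NQ there is not a maximum effect. Total NQs are set to zero, and keeping more zeros would make a geometric mean zero or undefined.

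**Conclusion.** The point holds for free CCL17. The stated rule drops isolated NQs that, after dosing on active drug, are the largest observable effect. It sits beside a footnote that includes them and, on the visible text, departs from Tables 4.01 and 4.06. The direction is fixed: omission never lowers the plotted geometric mean. With six active participants and the other values measurable, the rise is at least 12%, 26% or 41% for one, two or three isolated NQs.

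Anything beyond those minima is illustrative. The 2.61-fold ratio in the table needs three of six participants with isolated NQs at the same visit and the rest at an assumed 10 pg/mL. The documents give neither baseline free CCL17 nor NQ frequency, so the actual size cannot be determined and could be nil where NQs occur only in runs. Part B percentage reduction is model-derived, so there the point concerns mainly the concentration means. The figures are descriptive and the co-primary pain analysis does not use them. For total CCL17 the only issue is that individual figures retain measurable values after consecutive NQs while mean and median figures omit them.

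**What to change.** 1. In Figures 4.01–4.06, exempt free CCL17 from the single-NQ omission. Plot and summarise every free NQ at half LLOQ, as Tables 4.01 and 4.06 state, and add a reference line at 2.93 pg/mL.
2. Keep the single-NQ omission for GSK3858279 concentration and for total CCL17, and name the analyte in the footnote.
3. For total CCL17, state one rule for measurable values that follow consecutive NQs and use it in the individual, mean and median figures.
4. Check that Section 14.5.4 says the same.

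This is a footnote and programming change and needs no new data. The one trade-off is that an isolated free NQ caused by a sample or assay fault would also be kept at half LLOQ, as the visible table rule already does; the concentration listings let such a value be examined.

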14.11.11.2. Part B

No.	Population	IDSL / Example Shell	Title	Programming Notes	Deliverable
Serum Target Engagement					
4.04.	Safety	PK16	Part B: Individual Free & Total Serum CCL17 Concentration-Time Plots (Linear and Semi-log)	
One panel per dose group.
 
Add the following footnotes:
 
Note: Free CCL17 LLOQ = 2.93 pg/mL, ULOQ = 3600 pg/mL.
 
Note: Total CCL17 LLOQ = 13.11 pg/mL, ULOQ = 50000 pg/mL.
 
Note: The baseline value is presented at an actual relative time of 0 days.
 
Note: Any non-quantifiable (NQ) Free CCL17 concentration values have been set to $\frac{1}{2} \times \text{LLOQ}$.
 
Note: Any NQ Total CCL17 concentration values before the first measurable concentration have been set to 0 and have been included in the linear plot.
 
Note: Any single NQ values have been omitted.
 
Note: Any multiple mid-profile NQ concentrations of Free CCL17 and Total CCL17 have been set to $\frac{1}{2} \times \text{LLOQ}$ and 0, respectively, and the subsequent measurable concentrations have been retained.
 
Note: Percentage reduction values ≤ 0 are imputed to be 0.1 and values ≥ 100 are imputed to be 99.9.
	Part B SAC

No.	Population	IDSL / Example Shell	Title	Programming Notes	Deliverable
4.05.	Safety	PK17	Part B: Mean Free & Total Serum CCL17 Concentration-Time Plots (Linear and Semi-log)	
Apply logit transformation for % reduction parameter. If % reduction ≤ 0, set to 0.1. If % reduction ≥ 100, set to 99.9. These imputations are needed for logit transformation. Use Student's t-distribution for CI. Add the following footnotes: Note: Free CCL17 LLOQ = 2.93 pg/mL, ULOQ = 3600 pg/mL. Note: Total CCL17 LLOQ = 13.11 pg/mL, ULOQ = 50000 pg/mL. Note: Free CCL17 and Total CCL17 concentrations below LLOQ have been set to $\frac{1}{2} \times \text{LLOQ}$ and 0, respectively, and have been included in the summary statistic calculations. Note: Any single mid-profile non-quantifiable (NQ) concentrations have been omitted. Note: Measurable Total CCL17 concentrations following more than one consecutive mid-profile NQ have been omitted. Note: Zero Total CCL17 concentration values have been set to missing in the log-linear plot. Note: The geometric mean is plotted as the data is not normally distributed. Note: Percentage reduction values ≤ 0 are imputed to be 0.1 and values ≥ 100 are imputed to be 99.9. Note: The percentage reduction parameter was logit transformed, summarised, and back-transformed using the logistic function to obtain the geometric summary statistics.
	Part B SAC

No.	Population	IDSL / Example Shell	Title	Programming Notes	Deliverable
4.06.	Safety	PK18	Part B: Median Free & Total Serum CCL17 Concentration-Time Plots (Linear and Semi-log)	
Add the following footnotes:
 
Note: Free CCL17 LLOQ = 2.93 pg/mL, ULOQ = 3600 pg/mL.
 
Note: Total CCL17 LLOQ = 13.11 pg/mL, ULOQ = 50000 pg/mL.
 
Note: Free CCL17 and Total CCL17 concentrations below LLOQ have been set to $\frac{1}{2} \times \text{LLOQ}$ and 0, respectively, and have been included in the summary statistic calculations.
 
Note: Any single mid-profile non-quantifiable (NQ) concentrations have been omitted.
 
Note: Measurable Total CCL17 concentrations following more than one consecutive mid-profile NQ have been omitted.
 
Note: Zero Total CCL17-concentration values have been set to missing in the log-linear plot.
	Part B SAC

14.11.12. Biomarker Tables

14.11.12.1. Part A

No.	Population	IDSL/ Example Shell	Title	Programming Notes	Deliverable
Immune Cell Phenotype					
5.01.	Biomarker	BIO_T1	Part A: Summary of Immune Cell Phenotypes		Part A SAC
5.02.	Biomarker	BIO_T2	Part A: Analyses of Immune Cell Phenotypes: Treatment		Part A SAC
5.03.	Biomarker	BIO_T3	Part A: Analyses of Immune Cell Phenotypes: Sample Type		Part A SAC

14.11.13. Biomarker Figures

14.11.13.1. Part A

No.	Population	IDSL / Example Shell	Title	Programming Notes	Deliverable
Immune Cell Phenotype					
5.01.	Biomarker	BIO_F1	Part A: LS Mean Change from Baseline (+/- SE) of Immune Cell Phenotypes: Treatments by Visit		Part A SAC
5.02.	Biomarker	BIO_F2	Part A: Differences and 95% CI of Immune Cell Phenotypes: Treatments by Visit		Part A SAC
5.03.	Biomarker	BIO_F1	Part A: LS Mean Change from Baseline (+/- SE) of Immune Cell Phenotypes: Sample Type by Visit		Part A SAC
5.04.	Biomarker	BIO_F2	Part A: Differences and 95% CI of Immune Cell Phenotypes: Sample Type by Visit		Part A SAC

14.11.14. Efficacy Tables

14.11.14.1. Part B

No.	Population	IDSL / Example Shell	Title	Programming Notes	Deliverable [Priority]
Primary Efficacy					
6.01.	ITT	EFF_T10	Part B: Summary of Pain Intensity Data	Frequency table showing at each visit, how many subjects had how many days of knee pain intensity data (presented by trt group).	IA1, IA2, Part B SAC

[figure not shown]
No.	Population	IDSL / Example Shell	Title	Programming Notes	Deliverable [Priority]
6.02.	ITT	EFF_T1	Part B: Summary of Absolute Values and Change from Baseline in Average Knee Pain Intensity		IA1, IA2, IA3, IA4, Part B SAC
6.03.	ITT	EFF_T2	Part B: Bayesian Analysis of Change from Baseline in Average Knee Pain Intensity		IA1, IA2, IA3, IA4, Part B SAC
6.04.	PP	EFF_T1	Part B: Summary of Absolute Values and Change from Baseline in Average Knee Pain Intensity		Part B SAC
6.05.	PP	EFF_T2	Part B: Bayesian Analysis of Change from Baseline in Average Knee Pain Intensity		Part B SAC
6.06.	ITT	EFF_T1	Part B: Summary of Absolute Values and Change from Baseline in Worst Knee Pain Intensity		IA3, IA4, Part B SAC
6.07.	ITT	EFF_T2	Part B: Bayesian Analysis of Change from Baseline in Worst Knee Pain Intensity		IA3, IA4, Part B SAC

[figure not shown]
CCI

CONFIDENTIAL

207804

CCI

14.11.15. Efficacy Figures

14.11.15.1. Part B

No.	Population	IDSL / Example Shell	Title	Programming Notes	Deliverable [Priority]
Primary Efficacy					
6.01.	ITT	EFF_F1	Part B: Plot of Posterior Median and 95% CI of Average Knee Pain Intensity		Part B SAC
6.02.	ITT	EFF_F1	Part B: Plot of Posterior Median and 95% CI of Change from Baseline in Average Knee Pain Intensity		IA1, IA2, IA3, IA4, Part B SAC
6.03.	ITT	EFF_F1	Part B: Plot of Posterior Median and 95% CI of Worst Knee Pain Intensity		Part B SAC
6.04.	ITT	EFF_F1	Part B: Plot of Posterior Median and 95% CI of Change from Baseline in Worst Knee Pain Intensity		Part B SAC
6.05.	PP	EFF_F1	Part B: Plot of Posterior Median and 95% CI of Average Knee Pain Intensity		Part B SAC
6.06.	PP	EFF_F1	Part B: Plot of Posterior Median and 95% CI of Change from Baseline in Average Knee Pain Intensity		Part B SAC

CONFIDENTIAL

207804

No.	Population	IDS / Example Shell	Title	Programming Notes	Deliverable [Priority]
CCI					

14.11.16. ICH Listings

14.11.16.1. Part A

No.	Population	IDSL / Example Shell	Title	Programming Notes	Deliverable
Subject Disposition					
1.	Screened	ES7	Part A: Listing of Reasons for Screen Failure		Part A SAC
2.	Screened	ES9	Part A: Listing of Subjects who were Rescreened		Part A SAC
3.	Enrolled	ES2	Part A: Listing of Reasons for Study Withdrawal		Part A SAC
4.	Randomized	BL1	Part A: Listing of Subjects for Whom the Treatment Blind was Broken		Part A SAC
5.	Randomized	TA1	Part A: Listing of Planned and Actual Treatments		Part A SAC
Protocol Deviations					
6.	Enrolled	DV2	Part A: Listing of Important Protocol Deviations		Part A SAC
7.	Enrolled	IE3	Part A: Listing of Subjects with Inclusion/Exclusion Criteria Deviations		Part A SAC
Populations Analysed					
8.	Enrolled	SP3	Part A: Listing of Subjects Excluded from Any Population		Part A SAC
Demographic and Baseline Characteristics					
9.	Randomized	DM2	Part A: Listing of Demographic Characteristics		Part A SAC
10.	Randomized	DM9	Part A: Listing of Race		Part A SAC
Medical History					
11.	Safety	MH2	Part A: Listing of Current and Past Medical Conditions		Part A SAC

No.	Population	IDS / Example Shell	Title	Programming Notes	Deliverable
Concomitant Medications					
12.	Safety	CP_CM3	Part A: Listing of Prior and Concomitant Medications		Part A SAC
Exposure					
13.	Safety	POP_L01	Part A: Listing of Exposure Data		Part A SAC
Adverse Events					
14.	Safety	AE8CP	Part A: Listing of All Adverse Events		Part A SAC
15.	Safety	AE7	Part A: Listing of Subject Numbers for Individual Adverse Events		Part A SAC
16.	Safety	AE2	Part A: Listing of Relationship Between Adverse Event System Organ Classes, Preferred Terms, and Verbatim Text		Part A SAC
Serious and Other Significant Adverse Events					
17.	Safety	AE8CPa	Part A: Listing of Serious Adverse Events (Fatal and Non-Fatal)		Part A SAC
18.	Safety	AE14	Part A: Listing of Reasons for Considering as a Serious Adverse Event		Part A SAC
19.	Safety	AE8CP	Part A: Listing of Adverse Events Leading to Withdrawal from Study / Permanent Discontinuation of Study Treatment		Part A SAC
20.	Safety	AE8CP	Part A: Listing of Other Significant Adverse Events		Part A SAC
Vital Signs					
21.	Safety	VS4	Part A: Listing of Vital Signs of Potential Clinical Importance		Part A SAC
22.	Safety	VS4	Part A: Listing of All Vital Signs Data for Subjects with Any Value of Potential Clinical Importance		Part A SAC
Laboratory: All					
23.	Safety	LB5	Part A: Listing of Laboratory Values of Potential Clinical Importance		Part A SAC
24.	Safety	LB5	Part A: Listing of All Laboratory Data for Subjects with Any Value of Potential Clinical Importance		Part A SAC
25.	Safety	LB14	Part A: Listing of Laboratory Data with Character Results		Part A SAC

No.	Population	IDSL / Example Shell	Title	Programming Notes	Deliverable
26.	Safety	UR2A	Part A: Listing of Urinalysis Data for Subjects with Any Value of Potential Clinical Importance		Part A SAC
ECG					
27.	Safety	EG3	Part A: Listing of ECG Values of Potential Clinical Importance		Part A SAC
28.	Safety	EG3	Part A: Listing of All ECG Values for Subjects with Any Value of Potential Clinical Importance		Part A SAC
29.	Safety	EG5	Part A: Listing of Abnormal ECG Findings		Part A SAC
30.	Safety	EG5	Part A: Listing of All ECG Findings for Subjects with an Abnormal ECG Finding		Part A SAC
Telemetry					
31.	Safety	EG5	Part A: Listing of Abnormal Telemetry Findings	.	Part A SAC

